6.2 Patients characteristics

Demographic and baseline data:

- Age (years)
- Gender (male/female)
- Ethnic group (Arab; Caucasian; Latin; Asian; Black; Other)
- Weight (kg)
- Height (cm)
- Body surface area (BSA) (m²)
- Body mass index (BMI) - calculated

In addition to all the basal characteristics used in APLICOV-PC if it necessary.

7 Analysis of the primary endpoint

The main objective of the study is to evaluate the incidence of post-COVID-19 morbidity and characterize the profile of complications in the cohort of patients who participated in the APLICOV-PC study.

The number and percentage of patients who develop complications related to persistent illness, according to the physician, during the period between the end of the APLICOV-PC proof of concept study and the completion of this extension study by the patient, as well as the percentage of patients who present complications will be detailed.

A description of the following endpoints will be presented:

- Number and percentage of patients who required readmission to hospital and causes, since last visit of APLICOV-PC study until the end of this extension study.
- Number and percentage of patients who needed oxygen therapy and duration of the same, since last visit of APLICOV-PC study until the end of this extension study.
- The maximum, minimum, Q1 and Q3, mean, median and standard deviation (Std) of the duration of the oxygen therapy.
- Number and percentage of patients who presented complications (defined in Annex 5 of the protocol).
- Barthel Index. A description with the frequency and percentage of each dependency category, according to the score obtained, will be provided:
 - 0-20: Total dependency
 - 21-60: Severe dependency
 - 61-90: Moderate dependency
 - 91-99: Slight dependency
 - 100: Independence
- The maximum, minimum, Q1 and Q3, mean, median and Std of the parameters related to pulmonary function will be provided: oxygen saturation (SaO₂), ratio of partial pressure arterial oxygen and fraction of inspired oxygen (PAFI), forced vital capacity (FVC), forced expiratory volume in 1 second (FEV1), FEV1/FVC and diffusion test.

- The maximum, minimum, Q1 and Q3, mean, median and Std of the results of the Six-minute walk test (6MWT).
- Frequency and percentage of each category of the modified Medical Research Council (mMRC) scale:
 - 0 (Dyspnea only after strenuous exercise)
 - 1 (Dyspnea occurring when hurrying on level ground or walking up a slight incline)
 - 2 (Dyspnea resulting in walking more slowly than people of the same age on level ground or in stopping for breath when walking at own pace on level ground)
 - 3 (Dyspnea resulting in stopping for breath after walking about 100 meters or after a few minutes on level ground)
 - 4 (Dyspnea severe enough to prevent the person from leaving the house or occurring when dressing or undressing)
- In patients who present pneumonia upon entry into the APLICOV-PC study, number and percentage of patients with abnormalities in the chest X-ray and description of these abnormalities.
- Number and percentage of patients who presented abnormalities $\geq G2$ in the analytical parameters.
- Number and percentage of patients who presented abnormalities in the electrocardiogram (ECG) and description of these abnormalities.
- In patients suffering a relevant cardiac event during their participation in the APLICOV-PC study, number and percentage of patients who presented abnormalities in the heart Ultrasound/multigated acquisition scan (MUGA) and description of these abnormalities.
- Multivariate analysis to evaluate the relationship of the main covariates in the previous study (APLICOV-PC). More relevant exploratory covariates from the univariate analyses (p-value < 0.10) will be included in the multivariate analyses. The endpoints listed were correlated with the patients' basal characteristics, the degree of severity of the illness, comorbidities, the plitidepsin dosage, the viral load and the clinical evolution documented in the APLICOV-PC study.

8 Other analysis

- The maximum, minimum, Q1 and Q3, mean, median and Std of the vital signs will be provided: systolic blood pressure (SBP), diastolic blood pressure (DBP), heart rate (HR), temperature and respiratory rate.
- The maximum, minimum, Q1 and Q3, mean, median and Std of ECG parameters.
- Number and percentage of patients with abnormalities in the physical examination. The result will be listed.
- Number and percentage of patients with abnormalities in the neurological examination. The result will be listed.
- A description will be provided with the frequency and percentage of each category of the lung diffusion test:
 - Normal (between the 80 % and 120 % of the reference value)
 - Low (below the 80 % of the reference value)

- High (over the 120 % of the reference value)
- Number and percentage of patients who have been diagnosed of COVID-19 since the completion of APLICOV-PC study.
- Number and percentage of patients who have received any COVID-19 vaccine and the number of doses.
- Number and percentage of related or unknown post-COVID-19 complication. Worst per patient.
- Number and percentage of all post-COVID-19 complications. Worst grade per patient.
- Number and percentage of related post-COVID-19 complications. Worst grade per patient.
- Number and percentage of patients with at least AE.
- Number and percentage of patients with at least SAE.
- Number and percentage of patients with at least grade ≥ 3 AE.
- Number and percentage of patients with AEs by system organ classes (SOC) and preferred term (PT), regardless of relationship.
- The maximum, minimum, Q1 and Q3, mean, median and Std of laboratory parameters.
- Aplicov-pc summary of Demographic and Other Baseline Characteristics table of patients include in this study by dose and severity of disease.
 - Median (range) time from symptom onset to first plitidepsin administration, days
 - Number of comorbidities, n (%) (none, one, two or more)
 - Comorbidities, n (%) (Cardiac disease, Kidney disease, Liver disease, Lung disease (COPD), Asthma, Diabetes, Hypertension, Obesity)
 - Clinical status at randomization, n (%)
 - Vital signs, median (range) (Body temperature, $^{\circ}\text{C}$, Systolic blood pressure, mmHg,
 - Diastolic blood pressure, mmHg, Heart rate, bpm, Respiratory rate, bpm, SpO2
 - B, %, On oxygen at baseline, n (%))
 - Laboratory parameters, median (range) (WBC, $\times 10^9/\text{L}$, Platelet count, $\times 10^9/\text{L}$, Lymphocytes, $\times 10^9/\text{L}$, Serum creatinine, $\mu\text{mol}/\text{L}$, ALT \times ULN, AST \times ULN, LDH \times ULN, CPK \times ULN, GGT \times ULN, C-reactive protein, Ferritin, D-dimer)
 - log10 copies/mL viral load, median (range)
 - Days from Plitidepsin to first complication
 - Days from hospital discharge to first complication
 - Time from Plitidipesin first-dose to E-APLICOV inclusion (Month)

9 Listing

- Post-COVID-19 complications will be listed.
- Hospital readmission will be listed
- Oxygen therapy will be listed
- The medication administered before starting the 6MWT will be listed.
- The results of the ECG will be listed.

- The results of the chest X-ray will be listed.
- The ECHO/MUGA results will be listed
- The hematological laboratory parameters will be listed.
- The coagulation laboratory parameters will be listed.
- The biochemistry laboratory parameters will be listed.
- The pharmacological treatments will be listed
- The AEs will be listed
- Physical examination will be listed
- The neurological examination will be listed
- The vaccination schedule will be listed
- The COVID-19 (PCR) will be listed
- The COVID-19 history will be listed
- The serology SARS-CoV-2 will be listed

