infection, in recovered patients [19-21]. According to an electronic follow-up record of 236,379 patients during the first six months following COVID-19 diagnosis, neuropsychiatric complications emerge in 34% of cases, not including cephaea. The most common complications include mood and anxiety disorders and psychoses (24%), neuropathies (2,1%), ischaemic heart disease (2.8%) and dementia (0.67%) [22]. On the other hand, the most frequent neurological symptoms are cephaea and cognitive changes, described in up to 68% and 81% of patients, respectively, with some sort of neurological symptom after week 12 following acute infection [23]. Cognitive changes that are usually reported are lack of concentration, attention, or difficulty planning tasks.

The rapid drop in viral load of patients with COVID-19 infection may reduce the frequency of complications caused by the infection in the following months [24].

The WHO European Observatory on Health Systems and Policies estimates that 10% of infected patients remain symptomatic for at least 12 weeks after infection, resulting in long-term sick leave, leaving sequelae that in 0.8% even last more than a year [25]. A study in Spain, based on Social Security data, shows that COVID caused 1.2 million registered sick leaves by March 2021, and its authors indicate that nearly 100,000 people needed 12 weeks or more to recover from post-COVID sequelae. The casualties were justified by almost 50 different symptoms ranging from fever, shortness of breath, fatigue, anxiety, dizziness or memory loss.

On the other hand, data has been published from the COVERS CAN study conducted in the United Kingdom [25], which carried out serial Magnetic Resonance Imaging (MRI) scanning in a sample of 201 generally-healthy, middle-aged individuals, with COVID-19. The investigators found evidence of mild organ impairment of the heart (32%), lungs (33%), kidneys (12%), liver (10%), pancreas (17%), and spleen (6%) and reported that nearly 70% of the individuals suffered impairment in one or more organs 4 months after the initial symptoms of SARS-CoV2 infection, which was higher than age-matched healthy controls.

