5.2. Justification of the study

As previously indicated, the APLICOV-PC proof of concept study demonstrated the antiviral activity of plitidepsin in terms of reducing viral load, inducing recovery, and impact on lymphocyte reconstitution and other inflammatory parameters.

A percentage of patients, which varies between 10 and 25%, continue to show symptoms at 3 months after contracting the SARS CoV2 infection: For some of them this significantly restricts their life, requiring them to take long-term sickness leave from work, and leaving them with sequelae that may continue for more than one year.

With this study, we intend to evaluate whether the treatment with plitidepsin, by attaining a reduction in the viral load and a faster recovery of the patient, could have a relevant impact on the emergence of sequelae resulting from the SARS CoV2 infection.

5.3.Study objectives

Evaluate the incidence of post-COVID morbidity and characterise the complications profile in patients who participated in the APLICOV-PC study.

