12.2. Sample size

The main objective of the study is to evaluate the incidence of post-COVID morbidity and characterize its profile in patients who participated in the APLICOV-PC study. Given that a total of 45 patients received plitidepsin in said study, of which 3 died as a consequence of the progression of the disease, the maximum number of patients who could participate in the study is limited to 42.

Assuming an average incidence of post-COVID complications of 15%, this study would have a power of 80% for detecting a reduction of 10%: if 3 or less patients presented post-COVID complications, the study would reject the null hypothesis (incidence of post-COVID complications: 15%) and would accept the alternative (5%), with an alpha error of 0.05 (unilateral).

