Categorical Endpoints (6MWT)	Severity of disease			
	Mild N=X	Moderate N=X	Severe N=X	Total N=X
n (%)				
Pre-TEST				
Borg scale of dyspnea and fatigue at basal (1):				
Post-TEST				
Borg scale of dyspnea and fatigue after test (1):				
Results				
Stopped or paused				

Other symptoms at the end of the exercise (2)				

(1) 0 (None); 0.5 (Very, very slight); 1 (Very slight); 2 (Slight); 3 (Moderate); 4 (Somewhat severe); 5 (Severe); 6 (Severe); 7 (Very severe); 8 (Very severe); 9 (Very very severe); 10 (Maximal).
 (2) Angina; Dizziness; Pain in hip, leg or calf; None

Listing 11.4 Abnormalities in the chest X-ray

Dose cohort	Subject id.	Date	Radiography result	Specify	Other

Listing 11.5 ECG Abnormalities

Dose cohort	Subject id.	Date	ECG Result	Specify	QT	PR	RR

Listing 11.6 ECHO/MUGA results

Dose cohort	Subject id.	Date	Result	Specify

Listing 11.7 Six-minute walk test results

Dose cohort	Subject id.	Date	Total distance	Number of laps	Stopped or paused	Reason for stopping or pausing

Listing 11.8 Six-minute walk test previous medication

Dose cohort	Subject id.	Date	Active ingredient	Admin. hour	Admin. minutes	Dose

Listing 11.9 Six-minute walk test. Supplementary oxygen during the test

Dose cohort	Subject id.	Supplementary oxygen needed?	Flow type	Flow type specify	Flow

Table 11.11 Patients with abnormalities in the chest X-ray (all patients)

	Dose Cohort			
	1.5 mg N=X	2.0 mg N=X	2.5 mg N=X	Total N=X
	n (%)			
Patients with abnormalities in the chest X-ray				

Table 11.12 Patients who presented abnormalities in the heart Ultrasound/MUGA (all patients)

	Dose Cohort			
	1.5 mg N=X	2.0 mg N=X	2.5 mg N=X	Total N=X
	n (%)			
Patients who presented abnormalities in the heart Ultrasound/MUGA				

Table 11.13 Multivariable analysis

Variable	Value	DF	Estimate	Standard error	Wald Chi-Square	Pr > Chi-Square	Effect	Odds Ratio Estimate	Lower 95% Confidence Limit for Odds Ratio	Upper 95% Confidence Limit for Odds Ratio

12 Other analysis

Table 12.1 Vital signs

Continuous endpoints	Dose Cohort											
	1.5						...				Total	
	N	Mean	Median	Range	Q1	...*
SBP (mmHg)												
DBP (mmHg)												
Heart rate (bpm)												
Temperature (°C)												
Respiratory rate (breaths/min)												

* Q3 and Std.

Table 12.2 Physical and neurological examination

Endpoints	Dose Cohort			
	1.5 mg N=X	2.0 mg N=X	2.5 mg N=X	Total N=X
	n (%)			
Physical examination				
Normal				
Abnormal				
Neurological examination				
Normal				
Abnormal				

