...				

Each patient reported once per Preferred Term (PT);

Table 12.9 Summary of AEs, regardless of relationship by SOC and PT by grade and overall. Worst grade per patient. (Dose 1.5 /2 /2.5 mg and total)

AEs		G1		G2		G3			Total	
		N	%	N	%	N	%	N	%	N	%
Gastrointestinal disorders	Abdominal pain										
	...										
	...										
										

Listing 12.8 All adverse events

Dose cohort	Subject id.	Age	SOC	PT	Serious adverse events	Relationship	Grade	Onset date	End date

Table 12.10 APLICOV - Patient description

	Dose Cohort			
	1.5 mg N=X	2.0 mg N=X	2.5 mg N=X	Total N=X
Age, median (range) years				
Gender, % male				
Median (range) time from symptom onset to first administration, days				
Number of comorbidities, n (%)				
None				
One				
Two or more				
Comorbidities, n (%)				
Cardiac disease				
Kidney disease				
Liver disease				
Lung disease (COPD)				
Asthma				
Diabetes				
Hypertension				
Obesity				
Clinical status at baseline, n (%)				
Mild COVID-19 infection				
Moderate COVID-19 infection				
Severe COVID-19 infection				
Vital signs, median (range)				
Body temperature, °C				
Systolic blood pressure, mmHg				
Diastolic blood pressure, mmHg				
Heart rate, bpm				
Respiratory rate, bpm				
SpO ₂ at room air, %				
On oxygen at baseline, n (%)				

	Dose Cohort			
	1.5 mg N=X	2.0 mg N=X	2.5 mg N=X	Total N=X
Laboratory parameters, median (range)				
WBC, $\times 10^9/\text{L}$				
Platelet count, $\times 10^9/\text{L}$				
Lymphocytes, $\times 10^9/\text{L}$				
Serum creatinine, $\mu\text{mol}/\text{L}$				
ALT, $\times \text{ULN}$				
AST, $\times \text{ULN}$				
LDH, $\times \text{ULN}$				
GGT, $\times \text{ULN}$				
CPK, $\times \text{ULN}$				
Ferritin (ng/mL)				
D-dimer (ng/mL)				
C-reactive protein (mg/L)				
\log_{10} viral load, median (range) copies/mL				
Days from Plitidepsin to first complication				
Days from hospital discharge to first complication				
Time from Plitidepsin first-dose to E- APLICOV inclusion (month)				

(*) Further covariates could be added upon request

Table 12.11 APLICOV - Patient description by severity of disease

	Dose Cohort			
	Mild N=X	Moderate N=X	Severe N=X	Total N=X
Age, median (range) years				
Gender, % male				
Median (range) time from symptom onset to first administration, days				
Number of comorbidities, n (%)				
None				
One				
Two or more				
Comorbidities, n (%)				
Cardiac disease				
Kidney disease				
Liver disease				
Lung disease (COPD)				
Asthma				
Diabetes				

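### SAP section 7 keeps covariates with univariate p<0.10, and Table 11.13 prints 95% odds-ratio limits that ignore this selection, so retained results mislead, although the table is exploratory and drives no decision

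*SAP*

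**What the plan says.** The last item of SAP section 7 plans a multivariable analysis of factors from the parent study: "More relevant exploratory covariates from the univariate analyses (p-value < 0.10) will be included in the multivariate analyses". It names six groups of factors: baseline characteristics, severity, comorbidities, dose, viral load and clinical course. The Table 11.13 shell (SAP Appendix II) has columns for estimate, standard error, Wald chi-square and its p-value, odds ratio, "Lower 95% Confidence Limit for Odds Ratio" and the matching upper limit.

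Neither document provides a cap on terms, penalisation, shrinkage, resampling, a multiplicity rule or a caution about these limits. Table 11.13 names no outcome, although Table 11.1.1 has three complication rows (related or unknown, regardless of relationship, related). Protocol section 12.4 says only that the endpoints are correlated with these factors, so the p<0.10 screen is a choice made in the SAP.

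**The concern.** A covariate enters the model only if the data already make it look associated with the outcome. Its interval is then computed from the same data as if it had been chosen in advance. An unrelated factor that passes therefore gets limits that exclude 1 far more often than 5% of the time, and a real factor that passes gets an inflated odds ratio.

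The factors include dose, severity and viral load. The study asks whether a faster fall in viral load reduces sequelae (Protocol section 5.2), and Table 11.13 is where a reader would look for that link. Such a reader could not tell a chance finding from an exaggerated real one.

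**Working it through.** **1. The plan's own figure.** No calculation supports the multivariable model. The only design calculation is in Protocol section 12.2: reject if 3 or fewer of 42 have complications. Exact binomial: P(X≤3 | 42, 0.15) = 0.107 and P(X≤3 | 42, 0.05) = 0.843, against the stated 0.05 and 80%. That mismatch is a separate matter. Only N = 42 and the rates are used below.

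**2. Number of events.** Protocol 12.2: 0.05×42 = 2.1 and 0.15×42 = 6.3. Protocol 5.2, "A percentage of patients, which varies between 10 and 25%, continue to show symptoms at 3 months": 4.2 to 10.5. Protocol 5.1, "neuropsychiatric complications emerge in 34% of cases": 0.34×42 = 14.3; and "nearly 70% of the individuals suffered impairment in one or more organs": 0.70×42 = 29.4. The check uses 2, 4, 6, 10, 14 and 29 events.

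**3. Assumptions not in the documents.** One outcome; 4 to 33 candidates (33 is the count of baseline rows in Table 12.10, an assumed upper end); one third of covariates binary at 30%, the rest normal; correlation 0 or 0.3; Wald test for the screen.

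**4. Benchmark.** For one unrelated covariate in a large sample, P(p<0.05 | p<0.10) = 0.05/0.10 = 50%. Small samples and crowded models dilute this.

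**5. Retained unrelated covariates.** Percentage of 95% Wald limits that exclude 1; 2,000 simulated trials per cell; separated models left out; correlation 0 / 0.3:

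| Events | 4 candidates | 10 candidates | 33 candidates |
|---|---|---|---|
| 2 | 6.5 / 4.1 | 7.2 / 4.6 | 4.4 / 3.0 |
| 4 | 30.1 / 23.0 | 22.2 / 16.4 | 9.9 / 7.1 |
| 6 | 39.1 / 32.1 | 32.1 / 23.3 | 22.0 / 12.4 |
| 10 | 40.6 / 35.3 | 38.8 / 26.6 | 29.6 / 15.9 |
| 14 | 45.4 / 32.9 | 40.0 / 25.2 | 33.0 / 17.2 |
| 29 | 37.8 / 33.6 | 37.3 / 26.1 | 31.2 / 15.1 |

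The rate falls with more candidates because overfitted models give very wide limits or separate, not because inference improves. At 2 events, 2-26% of final models separate (29-87% with a likelihood-ratio screen).

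**6. Sensitivity at 6 events.** Likelihood-ratio screen: 8-30%. Unpenalised profile limits in place of Wald limits: 18-63%, so the point does not depend on reading Table 11.13 as Wald limits. A second simulation with independent normal covariates gave 37.6% (4 candidates) down to 12.8-15.5% (33); with correlation 0.3 and 33 candidates, 9-11%; with binary covariates only and a Wald screen, 25-43%. Binary covariates with a likelihood-ratio screen mostly separate and give no usable limits.

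**7. Per candidate considered.** Retention rate × miss rate among those retained, in the second simulation: 0.09×0.376 = 3.4% (4 candidates) and 0.09×0.128 = 1.2% (33). Further runs at 6 events gave about 1-3%, below 5%.

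**8. Real effects (normal covariate, odds ratio per SD).** At 15% incidence, a true 1.5 is retained in 20-22% of trials with median reported value 3.0-3.1; a true 2.0 is retained in 40-42% and reported as 3.3-3.5. At 34% incidence the reported values are about 2.4 and 2.6-2.7. Without selection the medians are 1.5-1.6 and 2.1. Limits for real effects miss in 1-8%, so the coverage failure concerns unrelated covariates.

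**9. Without the screen, 6 events.** One or two prespecified covariates, ordinary logistic model: miss 3.2% and 3.4%; a true 1.5 has median 1.53 and 1.55. The excess comes from the screen. Firth model with two terms (six assumed splits of dose and severity): miss 3-6% per term. Firth models one factor at a time: 3.7-4.3%.

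**The case against.** The strongest objection is that the 12-40% is conditional. It counts only unrelated factors that have already passed p<0.10, and a high rate among those is built in. Per factor considered, the screen plus the model is stricter than a single 5% test. This stands: a reader might infer that the SAP inflates the false-positive rate for each factor, and step 7 shows that it does not.

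The table is also exploratory. SAP section 7 uses that word for the covariates, and Protocol section 12.1 calls the analyses mainly descriptive. That lowers the priority, but the word does not make a 95% limit cover 95%, and the Table 11.13 shell carries no such label.

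The candidate list is uncertain. SAP section 6.2 adds "In addition to all the basal characteristics used in APLICOV-PC if it necessary" and a footnote to Table 12.10 says "Further covariates could be added upon request", but both concern patient description, and section 7 speaks of the main covariates. The documents do not say that 33 factors will be screened. Dropping the upper end does not help, since the miss rate is higher with fewer candidates.

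Finally, showing factors singly gives a higher chance of at least one false exclusion than the SAP procedure, and rows that exclude 1 still exaggerate: among such Firth intervals at 15% incidence, a true odds ratio of 1.5 has a median of 2.9. This also stands. That part of the remedy works only through full display and labelling.

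**Conclusion.** The point holds for what Table 11.13 will report. At 6 events with a Wald screen, 4-33 candidates and correlation 0-0.3, retained unrelated covariates have limits that exclude the truth in about 12-40% of cases. A retained true odds ratio of 1.5 per SD is reported as about 3 at 15% incidence. The size depends on the event count, screening test, candidate number and covariate type, none of which the SAP fixes. At 2 events the coverage failure nearly disappears and separation takes its place.

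A reader might infer that the main result is compromised. The documents do not support that: the incidence estimate does not use this model, and the rule in Protocol section 12.2 does not refer to it. This is a low-to-moderate priority correction to an exploratory table.

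**What to change.** In SAP section 7:

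- Delete the p<0.10 screen.
- Prespecify one model of about two terms, chosen and coded by the sponsor before analysis (for example dose and baseline severity), for one named complication row of Table 11.1.1.
- Fit it by Firth penalised logistic regression, and put profile-likelihood 95% limits in Table 11.13 in place of the Wald columns.
- Show the other factors listed in Protocol section 12.4 one at a time as Firth odds ratios with 95% limits and no p-values. Print all of them whatever the result, state how many are shown, and label them hypothesis-generating.
- State that no conclusion rests on a single interval that excludes 1.

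The cost is SAP wording, one table shell and two SAS options (FIRTH, CLODDS=PL); no new data are needed.

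Downsides to state: fewer factors are adjusted for jointly; one term per factor assumes a trend across doses or severity grades; and intervals are very wide with few events. At 6 events under the null, at least one of the two model terms excludes 1 in 7-10% of trials. At least one single-factor interval does so in 22-23% with 6 factors (13-15% under the SAP procedure), 32-34% with 10 (17-22%) and 62-72% with 33 (23-37%). The count and the label are therefore part of the fix.

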7. SCREENING OF PATIENTS

All patients who participated in and received plitidepsin in the APLICOV-PC study are eligible candidates for participating in this extension study. The investigative team will contact the patient to agree a date for the medical visit. The patient will be invited to participate in the study, and be handed the Patient Information Leaflet for the same, along with all additional information related to the study that is necessary for obtaining their informed consent.

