8.2. Replacement of subjects and reserve subjects

Not applicable. Given the characteristics of the study, those patients who do not agree to participate in the study, or who withdraw their consent, cannot be replaced.

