5.5 Deaths

The number and percentage of patients who died during the study will be provided. Patients who have died due to an AE will be described in more detail, indicating all the variables related to the AEs registered in the electronic case report form (eCRF).

All the analyses will be performed separately for each arm and a total column will be added.

6 Patients description

6.1 Demographic data description. General considerations.

The characteristics of the patients will be described and the unavailable information will be detailed; not available values will not be taken into account in the percentage calculation, only valid percentages will be presented. The analysis will be carried out on the full population and all results will be provided by treatment arm. Aggregated results as well as patient listings will be provided.

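### The SAP reports incidence only for the APLICOV-PC survivors who consent about a year later, and does not examine selection into the extension, including death after the parent study

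*SAP*

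**What the plan says.** **Target and frame.** Protocol 5.3 and 12.4 and SAP 7 set the objective as incidence in patients who took part in APLICOV-PC. Protocol 12.2 makes this a closed list: "a total of 45 patients received plitidepsin in said study, of which 3 died as a consequence of the progression of the disease", so "the maximum number of patients who could participate in the study is limited to 42".

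**Entry.** Protocol 7 makes every plitidepsin-treated patient a candidate: "The investigative team will contact the patient to agree a date for the medical visit". The patient is then invited and asked for consent. Protocol 5.1 places the last parent inclusion in November 2020, and Protocol 1.14 sets extension enrolment for October to December 2021. Under Protocol 8.2, "those patients who do not agree to participate in the study, or who withdraw their consent, cannot be replaced".

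**Analysis set.** Protocol 12.3 and SAP 5.1 both require consent and agreement to the test battery.

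**Reporting.**
- SAP Table 10.1 counts patients analysed, Table 10.2 recruited and analysed by site, and Table 10.3 end-of-study reasons. None counts patients eligible, refused, unreachable or dead before consent.
- SAP 5.5 limits deaths to the extension: "The number and percentage of patients who died during the study will be provided".
- SAP 8 restricts the parent-study baseline table to enrolled patients: "Aplicov-pc summary of Demographic and Other Baseline Characteristics table of patients include in this study by dose and severity of disease". Shells 12.10 and 12.11 follow from it.
- SAP 4 states that there is no method for missing data, although Protocol 12.1 left the handling of unavailable data to the SAP.

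**The concern.** The question is about the treated cohort, but the answer comes from volunteers. The primary endpoint window opens at the end of APLICOV-PC (SAP 7), whereas a patient is seen only if alive, reachable and willing months later. A survivor who died, refused or could not be found in that interval leaves both numerator and denominator without being recorded.

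Selection could act in either direction. The most impaired may be unable to attend a visit with walk, lung-function and imaging tests, which would lower the observed incidence. The fully recovered may see no reason to come, which would raise it.

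What is at stake is the label on the result. A percentage among participants can be read as the incidence after plitidepsin and set against the 15% reference in Protocol 12.2, with no information on whether the people behind it resemble the cohort.

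**Working it through.** **Inputs.** From Protocol 12.2: 45 treated, 3 dead, ceiling N = 42, null 15%, alternative 5%, cut-off of 3 or fewer events, one-sided alpha 0.05, power 80%. Assumed, because the documents do not give it: m, the number analysed, from 30 to 42. Also assumed: 3 events, which is the Protocol's cut-off and not a forecast.

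**1. The plan's own figures.** Exact binomial with N = 42 and cut-off 3:
- P(X ≤ 3 | 0.15) = 0.107, against the stated 0.05.
- P(X ≤ 3 | 0.05) = 0.843, against the stated 80%.

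They do not reproduce. A cut-off of 2 gives 0.038 and 0.649. This is a separate defect and carries no weight here. What matters for this point is that the rule is set for the full ceiling of 42.

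**2. Bounds over the 42.** With x events among m analysed:
- lower bound = x/42 (no non-participant affected)
- upper bound = (x + 42 − m)/42 (all affected)
- width = (42 − m)/42, whatever x is

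With x = 3:

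| m | Observed 3/m | Lower 3/42 | Upper | Width (points) |
|---|---|---|---|---|
| 42 | 7.1% | 7.1% | 3/42 = 7.1% | 0 |
| 40 | 7.5% | 7.1% | 5/42 = 11.9% | 4.8 |
| 38 | 7.9% | 7.1% | 7/42 = 16.7% | 9.5 |
| 35 | 8.6% | 7.1% | 10/42 = 23.8% | 16.7 |
| 30 | 10.0% | 7.1% | 15/42 = 35.7% | 28.6 |

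Sampling error comes on top. The exact two-sided 95% interval for 3/42 is already 1.5% to 19.5%.

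**3. Where the bounds reach the null.** 15% of 42 is 6.3, so 3 + k must exceed 6.3. Three non-participants give 6/42 = 14.3%, and four give 7/42 = 16.7%. Four suffice.

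**4. The fixed cut-off with fewer patients.** If 3 is kept as the cut-off, P(X ≤ 3 | 0.15) rises from 0.107 at m = 42 to 0.130 at 40, 0.158 at 38 and 0.322 at 30.

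**5. Direction.** Take a true rate of 15% and let participation differ by outcome.
- 60% of affected and 90% of unaffected take part: 0.15 × 0.60 = 0.090 and 0.85 × 0.90 = 0.765. Apparent incidence 0.090/0.855 = 10.5%, with 42 × 0.855 ≈ 36 participants.
- 90% of affected and 70% of unaffected: 0.135 and 0.595. Apparent incidence 0.135/0.730 = 18.5%, with 42 × 0.730 ≈ 31 participants.

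**6. Deaths after the parent study.** The endpoint is physician-judged complications of persistent illness (SAP 7), and Protocol Annex 5 does not list death. Suppose m = 38 and one of the four non-participants is known to have died. Counting that death as a complication gives an upper bound of 7/42 = 16.7%. Showing it separately gives 6/42 = 14.3% plus 1/42 = 2.4% dead. The two treatments fall on opposite sides of 15%, so the rule has to be written down.

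**The case against.** Several objections have force.

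- **Data access.** The documents nowhere say that the sponsor can use parent data on all 45 for this study. They show parent data being used for enrolled patients and give the counts of treated and dead. Access for the rest is a reasonable inference, not a stated fact. This stands, and the comparison column depends on it.
- **Permissions.** Refusal reasons and later vital status are new information about people who have not consented. Protocol 14.5 requires explicit consent before data collection where necessary, and Protocol 13.6 allows only minimal data even for someone who enrols and withdraws. This stands. The reasons can be reported only as far as records and permissions allow.
- **Already derivable.** A reader might infer that selection cannot be judged at all. That goes too far: the participation rate and the crude bounds follow from the number in Table 10.1 and the ceiling of 42. What cannot be derived is who is missing and why.
- **Importance.** A reader might also infer that participation was low, or that the incidence is biased downwards. No passage supports either. If all 42 enrol, the bounds collapse to a single value.
- **Descriptive study, small column.** The analyses are mainly descriptive, and the analysis set is openly defined as consenters. At 30 to 40 participants, the comparison column holds only 12 to 2 patients, which is imprecise and at the small end may risk re-identification. That argues for pooling over doses. It does not argue for silence, because a descriptive incidence depends directly on its denominator.

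ICH listing 16.2.3 in SAP 14, for patients left out of the efficacy analysis, does not close the gap. Nothing extends it to parent patients who never enrolled, and a listing supplies neither a comparison nor bounds.

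**Conclusion.** The point holds. The objective refers to the plitidepsin-treated cohort, 42 survivors of 45. The analysis set, disposition, deaths and parent-baseline tables cover only those who consent. The planned percentage is therefore an incidence among participants, and selection into the extension, including death after the parent study, goes unexamined.

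The size depends on participation, which the documents do not give. Each non-participant widens the bounds by 1/42, or 2.4 points. Under an assumed 3 events the range is 7.1% to 11.9% at 40 participants and 7.1% to 35.7% at 30, and it takes in the 15% null from four non-participants onwards. These are worst-case limits, not estimates of bias, and the direction of any bias is unknown. The point limits what may be concluded about the cohort. It does not show the participants' result to be wrong.

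**What to change.** 1. **Flow table.** Report 45 treated, 3 died, 42 eligible, enrolled, analysed. Split non-enrolment into refused, unreachable, known to have died since, and unknown, as far as site records and data permissions allow.
2. **Comparison.** Add a 'not enrolled' column to Table 12.10 with age, sex, severity, comorbidities, viral load and dose from the parent database, assuming the sponsor can access it for all treated patients. Pool it over doses, because numbers will be small.
3. **Bounds.** Under Table 11.1.1, state that the primary percentage refers to participants. Add best- and worst-case incidence over the 42. Show known later deaths as a separate category, not silently counted as complications.

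**Cost.** One table, one column and a few rows; no new visit or test. SAP v2.0 itself added Tables 12.10 and 12.11, so a change of this kind is practicable. The bounds need only the number analysed and the event count. The downsides are a less favourable upper bound on display, a small and imprecise comparison column, and the chance that some non-participant data, later vital status above all, will be unavailable.
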